12. Comparison between the efficacy of risankizumab, as assessed according to the primary endpoint of the study, when used as second, third or fourth line of biological treatment.
13. Assessment of the safety of risankizumab during the entire study period.

3. Study design and investigational plan

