4.3. Exclusion criteria

1. Age < 18 years.
2. Patients with diagnosis of indeterminate IBD.
3. Patients naive to advanced (biological or small molecule) therapy for IBD.
4. Refusal to sign written informed consent certifying the willingness of the subject to participate to the study.

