4.4. Sample size evaluation and statistical analysis

Based on the real-life study design and on the primary endpoint, which foresees a descriptive evaluation of remission rates according to each therapy line considered, we present diverse scenarios of potential sample size (from 50 till 300 by 25), and related confidence intervals in order to detect a CPDR at 12 months of 50-55 and 60% according to the evidence available from the current literature on the drugs under investigation. All scenarios are assessed according to a single group study design with a two-sided 95% confidence interval for a single proportion. A table with all potential scenarios will be provided as attachment.

As an example, such single-group design to obtain a two-sided 95% confidence interval for a single proportion, assuming a sample proportion of 0.5, with a sample size of 50, would produce a confidence

interval width of 0.28945, i.e., 0.5 ± 0.145 . The confidence interval widths were computed using PASS 2022, version 22.0.4 [29].

Based on the data available to the participating centers (for the retrospective phase) and the recruitment capabilities of the centers during the enrollment period, we expect to enroll 200 subjects with Crohn disease in this retrospective study.

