The evaluation of the difference in terms of CPDR at 12 months and 24 months, respectively, according to the different biological sequential therapies at II and III lines will be evaluated by Kaplan-Meier survival analysis. In particular, the log-rank test will be applied and appropriate cumulative incidence curves will be drawn. The analysis will be performed using the R packages “*ggplot2*” and “*survminer*” [31,32].

Potential predictors of CPDR will be assessed by Cox regression models. In detail, the potential predictors of the outcome will be evaluated by means of ordinary proportional hazards Cox regression models, and the Hazard Ratios (HR) and the 95% confidence intervals (CIs) will be reported. The proportionality of the hazard functions will be evaluated by visual inspection of the hazards and Schoenfeld residual plots. In case of doubtful proportionality, Cox weighted regression models will be

fitted. The analysis will be performed with "*survival*" and "*coxphw*" R packages [33-37]. Whether possible due to the different sample sizes of each therapeutic line and sequential strategy, to evaluate the combined effects between drug and line of administration, multivariable interaction models will be fitted, one per each predictor, and the interaction hazard ratios (IHR) reported. In summary, the coefficients of the main effects (in exponential terms) will be interpreted as HRs of the outcome by considering a unit increase of the predictor in the reference category (first line) (HR_{predictor}) as for quantitative predictors, whilst as increase in the hazard of the outcome occurring, as compared with the (arbitrarily) chosen reference group for qualitative data. The interaction parameters (IHR) will be interpreted as difference (in HR terms) of variations of the predictors among the different lines (first line as reference category).

5. Study procedures

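### Endpoint 12 compares 12-month CPDR across second, third and fourth line, but the only CPDR group test fixed in section 4.4 covers sequential therapies at lines II and III and leaves fourth-line patients out

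*Protocol*

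**What the plan says.** Secondary aim 12 (section 2, Study aims) and endpoint 12 (section 2.2) call for a comparison of risankizumab on the primary endpoint, 12-month CPDR, "when used as second, third or fourth line of biological treatment".

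Section 4.4 brings in therapy line for CPDR in three places:

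- The sample-size paragraph foresees a "descriptive evaluation of remission rates according to each therapy line considered".
- The difference in CPDR at 12 and 24 months "according to the different biological sequential therapies at II and III lines will be evaluated by Kaplan-Meier survival analysis". The test is then named: "In particular, the log-rank test will be applied".
- If group sizes allow, "to evaluate the combined effects between drug and line of administration, multivariable interaction models will be fitted", with "first line as reference category".

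Section 4.3 excludes "Patients naive to advanced (biological or small molecule) therapy for IBD". The expected enrolment in section 4.4 is 200, and the planning values for CPDR are 50, 55 and 60%. They are not assigned to lines, and no power is stated for a comparison between lines.

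**The concern.** The endpoint and the test do not describe the same contrast. The endpoint has three groups defined by line. The test has groups described as sequential therapies, within two lines. Fourth-line patients are in the endpoint and absent from the test.

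If remission falls steadily with later line, the fourth line carries the largest contrast, and dropping it discards the most informative comparison. If groups are also cut by the drugs used earlier, a line effect is spread over more degrees of freedom. A non-significant result could then be reported as no difference by line when the fourth line was never tested. A significant one could come from a single small sequence and be read as a line effect.

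**Working it through.** **1. Endpoint against test.**

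| | Endpoint 12 (section 2.2) | CPDR group test (section 4.4) |
|---|---|---|
| Grouping | line of treatment | sequential therapies (literally, drug sequence) |
| Lines covered | second, third, fourth | II and III |
| Outcome | CPDR at 12 months | CPDR at 12 and 24 months, Kaplan-Meier and log-rank |

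Reading sequential therapies as shorthand for line gives line II against line III. The fourth line is still missing.

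**2. Do other parts of section 4.4 fill the gap?**

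- The rates by line are descriptive, while endpoint 12 is a comparison.
- The tests among lines in the paragraph on between-group differences are for AEs and SAEs; the other tests there concern baseline.
- The general Cox predictor models do not name line as the term that answers endpoint 12.
- The interaction models are conditional on group sizes and refer every contrast to first line. If line counts advanced therapies, section 4.3 leaves that category empty. If it counts biologics only, the category could hold only patients whose sole earlier advanced therapy was a small molecule. Endpoint 12 does not list a first line either way.

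**3. The protocol's own figure.** For p = 0.5 and n = 50, the exact (Clopper-Pearson) 95% interval for 25/50 is 0.3553 to 0.6447, width 0.28945, as stated.

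**4. Size, as an illustration.** From the protocol: N = 200. Assumed: all patients evaluable, two-sided 5%, the line splits, the gradients, equal-sized sequences and no drug effect within a line.

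For k groups the noncentrality is λ = Σ nᵢ(pᵢ − p̄)² / [p̄(1 − p̄)], with k − 1 df. Example with split 100/60/40 and CPDR 60/50/40%:

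- Three lines: p̄ = (60 + 30 + 16)/200 = 0.53. λ = (100 × 0.07² + 60 × 0.03² + 40 × 0.13²)/(0.53 × 0.47) = 1.22/0.2491 = 4.90. On 2 df, power is about 50%.
- Line II against III: p̄ = 90/160 = 0.5625. λ = (100 × 0.0375² + 60 × 0.0625²)/(0.5625 × 0.4375) = 0.375/0.2461 = 1.52. On 1 df, power is about 23%.
- Lines II–III cut by sequence: λ stays at 1.52 while the df rise. Power is about 16% with 4 sequences, 11% with 8 and 9% with 16.
- Trend, scores 2/3/4: mean score (200 + 180 + 160)/200 = 2.7. Σ nᵢ(sᵢ − 2.7)pᵢ = −42 + 9 + 20.8 = −12.2. The variance is 0.2491 × (49 + 5.4 + 67.6) = 30.39. |z| = 12.2/5.513 = 2.21, and power is about Φ(2.21 − 1.96) = 60%.

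Range over splits 67/67/66, 100/60/40 and 120/50/30:

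| Test | 60/50/40% | 60/55/50% |
|---|---|---|
| II–III by sequence (4 to 16 groups) | 9–16% | 6–7% |
| II against III | 21–24% | 9–10% |
| Three lines, unordered | 45–53% | 14–16% |
| Trend over three lines | 56–64% | 19–21% |

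Simulated log-rank tests (2,000 per scenario, CPDR assessed at months 6 and 12) agree at 60/50/40%: 12% for six sequences in lines II–III, 49–54% for three lines and 60–65% for trend.

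**5. Precision per line.** With 100/60/40 and 60/50/40%, the exact 95% CIs are 50–70% (60/100), 37–63% (30/60) and 25–57% (16/40).

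**The case against.** The strongest reply is that the log-rank sentence may simply mean by line. The rest of section 4.4 uses line as its grouping, and the protocol never defines groups by earlier drug. That is a fair reading, and it removes the loss from splitting by sequence. It does not bring the fourth line back.

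Second, endpoint 12 states no direction, so an unordered three-line test is valid. This stands. Choosing a trend test is a preference, worth about 4 to 11 points of power in the scenarios examined, and it can lose power if CPDR does not change in one direction with line.

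Third, the by-line evaluation is described as descriptive and no power is claimed. This also stands: low power contradicts nothing in the protocol, and reporting rates with CIs by line fits its precision-based framework.

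A reader might infer that the plan ignores line altogether, or that its wording is what leaves endpoint 12 with very little power. The documents support neither. Line appears in the descriptive rates and in the interaction models. The number of sequences is nowhere stated, so any low figure for a sequence test depends on an assumed layout. Within the protocol's own 50–60% range even the trend test reaches only about 20%, so there the limit is mainly sample size and effect size.

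**Conclusion.** The mismatch holds on the text alone: the only CPDR group test fixed in section 4.4 does not test endpoint 12, because it omits the fourth line and, read literally, groups by drug sequence. This is not detail left to a later plan, since section 4.4 fixes the groups, the lines and the test, and they conflict with the endpoint.

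The size depends on assumptions outside the protocol. With a 60/50/40% gradient, a test limited to lines II and III has roughly half the power of an unordered three-line test or less, and splitting by sequence lowers it further. With a 60/55/50% gradient every option lies at about 6 to 21%, and better grouping gains little. In that case the CIs by line should carry the interpretation. For a secondary endpoint this is a correction that should be made, not a threat to the primary analysis.

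**What to change.** In section 4.4:

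1. State that endpoint 12 is tested on 12-month CPDR with patients grouped by second, third and fourth line.
2. Report each line's CPDR rate with its 95% CI, and state that a non-significant test will not be reported as no difference by line.
3. Change the reference category of the line models from first to second line, and say whether line counts small molecules as well as biologics.
4. Label comparisons of drug sequences as exploratory.

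A single 1-df trend test with line scored 2/3/4 is a reasonable option. If it is chosen, it should be named in advance, and the rates by line would still show a pattern that is not monotone.

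The cost is wording in section 4.4. If each patient's earlier advanced therapies are recorded, as the eligibility criteria and endpoint 12 already require, no new data are needed.

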3.1. Overall study design

This is a multicenter, retrospective observational study with drug, including patients fulfilling inclusion and exclusion criteria, whom data required for the protocol are available.

We will include consecutive patients affected by CD, who have initiated Risankizumab and failed (already exposed) at least one mechanism of action (for anti TNF-alpha several molecules are allowed), until January 2024.

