2.1. Primary endpoint

Primary endpoint of the study is the proportion of CD patients achieving steroid-free clinical-practice-deep remission (CPDR) after 12 months from baseline of treatment with Risankizumab, defined as the combination of:

patient reported outcomes (PRO) (patients reported abdominal pain \leq 1 and average stool consistency \leq 5 on Bristol Stool Scale without use of oral/intravenous steroids (prednisone-equivalent or budesonide) in the last 3 months)

AND an objective parameter of inflammation:

Faecal calprotectin <150 mcg/g, OR SES-CD \leq 4 and at least a 2-point reduction vs baseline and no subscore >1 in any individual variable, OR transmural healing at MRI/CT scan enterography or intestinal ultrasound, defined as BWT \leq 3 mm with no signs of active disease.

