4.2. Inclusion criteria

The participants must fulfill the following criteria for participating in the study:

1. Age of at least 18 years.
2. Patients with a previous diagnosis of CD at least 3 months before baseline.
3. Patients who have failed at least one advanced (biological or small molecule) therapy for CD and who have experienced failure to at least one mechanism of action (failure is defined as primary failure, secondary failure, or intolerance).
4. Patients, with any grade of clinical or endoscopic disease activity who have started a therapy with risankizumab for CD based on clinical practice indication (primary loss of response, secondary loss of response, intolerance to the previous drug).
5. Written informed consent certifying the willingness of the subject to participate to the study.

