The sample will be described in its clinical and demographic characteristics by descriptive statistics techniques. In depth, qualitative data will be expressed as absolute and relative percentage frequency, whilst quantitative variables either by mean and standard deviation (SD) or median and interquartile range (IQR), as appropriate. To verify the Gaussian distribution of quantitative variables, the Shapiro-Wilk test will be applied. Eventual missing values (if <5%) will be treated by *imputeR* package, using multiple imputation with Lasso Regression methods centered on the mean for quantitative data, whilst classification trees for imputation by “*rpartC*” function, centered on the mode, i.e. most represented class object, will be applied on qualitative data [30]. The sample will be described in its clinical and demographic characteristics by descriptive statistics techniques. In depth, qualitative data will be expressed as absolute and relative percentage frequency, whilst quantitative variables either by mean and standard deviation (SD) or median and interquartile range (IQR), as appropriate. To verify the Gaussian distribution of quantitative variables, the Shapiro-Wilk test will be applied. Eventual missing values (if <5%) will be treated by *imputeR* package, using multiple imputation with Lasso Regression methods centered on the mean for quantitative data, whilst classification trees for imputation by “*rpartC*” function, centered on the mode, i.e., most represented class object, will be applied on qualitative data [30].

Between-group differences at baseline will be assessed by either the Chi-squared or the Fisher-Freeman-Halton's exact test for qualitative variables, whilst with either one-way ANOVA or non-parametric Kruskal Wallis will be applied to quantitative data. Pairwise comparisons will be performed by either Student's t test or Mann-Whitney U test, as appropriate, with “False Discovery rate” correction for multiple comparisons. AEs and SAEs will be assessed by descriptive statistics and compared among the different lines with the aforementioned inferential tests.

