5.1. Experimental procedures

Data will be retrieved from the electronic archives of all participating center. Each patient will be identified by a number who will avoid double insertion of the same patient and will ensure the anonymization of data. Collected data will be entered in an electronic case report form (RedCap) and will follow all the requirements of Italian privacy policy.

In depth, the standard points will be: induction of therapy (T0 - week 0); 12 weeks after the beginning of therapy (T1), 6 months after the beginning of therapy (T2), 12 months after the beginning of therapy (T3), and 24 months after the beginning of therapy (T4).

The following clinical data at each time-point will be collected, to calculate Harvey Bradshaw Index – general well-being, abdominal pain, number of liquid/soft stools, abdominal mass and extraintestinal manifestations for CD.

Endoscopic or radiologic monitoring of disease activity respectively by ileocolonoscopy or intestinal ultrasound or CT-scan or MRI-enterography will be collected at baseline and at 12 and 24 months after the start of therapy. Endoscopic disease activity will be assessed according to the SES-CD.

Steroid-free clinical practice deep remission (CPDR) will be defined based on patient reported outcomes (PRO) combined with an objective parameter of inflammation:

- patients reported abdominal pain ≤ 1 and average stool consistency ≤ 5 on Bristol Stool Scale without use of oral/intravenous steroids (prednisone-equivalent or budesonide) in the last 3 months;

AND

- Faecal calprotectin <150 mcg/g, OR SES-CD \leq 4 and at least a 2-point reduction vs baseline and no subscore >1 in any individual variable, OR transmural healing at MRI/CT scan enterography or intestinal ultrasound, defined as BWT \leq 3 mm with no signs of active disease.

6. Ethical aspects

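### Section 3.1 makes availability of protocol data an entry condition without limiting it to baseline, so the cohort can be selected on follow-up and the 12-month remission proportion may be inflated

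*Protocol*

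**What the plan says.** Protocol section 3.1 gives two descriptions of who enters. The study is one "including patients fulfilling inclusion and exclusion criteria, whom data required for the protocol are available". The next sentence reads "We will include consecutive patients affected by CD, who have initiated Risankizumab", with prior failure of at least one mechanism of action and a cut-off of January 2024. The data-availability condition is not repeated in the eligibility lists of sections 4.2 and 4.3, and the protocol does not define which data are required.

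The primary endpoint (section 2.1) is a single proportion: "Primary endpoint of the study is the proportion of CD patients achieving steroid-free clinical-practice-deep remission (CPDR) after 12 months from baseline". It needs patient-reported outcomes, absence of steroids over the preceding three months and one objective marker. Section 5.1 says "Data will be retrieved from the electronic archives of all participating center". It sets time points at baseline, 12 weeks, and 6, 12 and 24 months. Endoscopy or imaging "will be collected at baseline and at 12 and 24 months after the start of therapy".

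Section 4.2 also requires "Written informed consent certifying the willingness of the subject to participate to the study", and section 4.3 excludes for "Refusal to sign written informed consent certifying the willingness of the subject to participate to the study". On incomplete data, section 4.4 says "Eventual missing values (if <5%) will be treated by" an imputation package. The protocol does not say how patients who stop treatment before 12 months are counted.

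**The concern.** In a retrospective archive study, the person extracting the data can see whether the follow-up record exists before deciding to enter the patient. If the required data include the 12-month assessments, entry depends on something that happens after treatment starts. Patients who stopped risankizumab early, had surgery, moved to another centre or died are the least likely to have those assessments. The quantity estimated then shifts from remission among starters to remission among those who stayed under follow-up.

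The primary result is one uncontrolled proportion, so its meaning depends on its denominator. The background section justifies the study by saying that randomised trials leave out many real-life patients. An entry rule that filters on follow-up would bring a selection of its own into the real-world estimate.

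Consent may act in the same direction. It is asked of patients whose treatment has already begun, and the protocol makes no provision for those who have died or cannot be traced.

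**Working it through.** **1. The plan's own precision figure.** Section 4.4 gives a 95% interval width of 0.28945 for a proportion of 0.5 and n = 50. The exact (Clopper-Pearson) interval for 25 of 50 is 0.35527 to 0.64473, width 0.28945. The figure reproduces, so the stated precision is not in question.

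**2. Precision at the planned size.** Section 4.4 expects 200 subjects and considers rates of 50, 55 and 60%. The same method gives, for 200 patients:
- 50%: 0.4287 to 0.5713, half-width 7.1 points
- 60%: 0.5285 to 0.6685, half-width 7.0 points

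**3. Inflation formula.** Let q be the remission rate among included patients, f the share of starters left out, and r the remission rate among those left out. Then:
- rate among all starters = q(1 − f) + f·r
- inflation = q − [q(1 − f) + f·r] = f(q − r)

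The values of q (50% and 60%) are the ends of the range in section 4.4. The documents give neither f nor r. I assume f = 10 to 30%, and r = 0, 25% or equal to q.

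| q | f | r = 0 | r = 25% | r = q |
|---|---|---|---|---|
| 50% | 10% | 5.0 | 2.5 | 0 |
| 50% | 20% | 10.0 | 5.0 | 0 |
| 50% | 30% | 15.0 | 7.5 | 0 |
| 60% | 10% | 6.0 | 3.5 | 0 |
| 60% | 20% | 12.0 | 7.0 | 0 |
| 60% | 30% | 18.0 | 10.5 | 0 |

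(Inflation in percentage points.)

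Example: with q = 60% and f = 20%, the rate among all starters is 0.60 × 0.80 = 48% if r = 0, and 0.48 + 0.20 × 0.25 = 53% if r = 25%. The included patients show 60% in both cases.

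**4. When the bias matches the half-width of 7 points.** Solve f = 0.07/(q − r):
- r = 0: 0.07/0.60 ≈ 12% (q = 60%) and 0.07/0.50 = 14% (q = 50%)
- r = 25%: 0.07/0.35 = 20% and 0.07/0.25 = 28%

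The formula does not contain n, so a larger sample would narrow the interval without reducing the bias.

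**5. Whether other parts of the protocol repair it.** The imputation rule in section 4.4 applies to missing values in patients already entered. The Kaplan-Meier and Cox analyses in the same section can censor entered patients but cannot include people who were never entered. The same limit applies to any non-responder rule in a statistical analysis plan, because eligibility is fixed in the protocol.

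**The case against.** The clause can be read more narrowly. Section 3.1 does not say that outcome data must be complete at entry, and the eligibility lists contain no such criterion. Section 4.4 foresees missing values and uses methods that handle censoring. Section 3.2 speaks of a maximum participation of 24 months, which allows shorter follow-up. Read literally, the clause would demand the 24-month data too. If only baseline data were meant, it would remove no early failures. This stands as an alternative reading, but the protocol does not state it and each centre is left to choose.

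The direction is probable but not proved. Remission needs both good patient-reported outcomes and an objective marker. A symptomatic or steroid-treated patient can therefore be classed as not in remission without a marker, while a well patient without one cannot be classed as in remission. Dropping patients for a missing marker can then remove remitters and lower the rate. This also stands, and it affects the fix.

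A reader might infer three stronger things that the documents do not support:
- That early failures are certainly removed and the rate overstated by a known amount, such as 12 points. That figure needs both an assumed 20% left out and zero remission among them.
- That only living, attending patients can consent. Former attenders can be contacted, and the protocol does not say when or how consent is sought from patients already treated.
- That the comparison by treatment line is biased because later lines drop out more. The documents contain nothing on dropout by line.

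The two sentences in section 3.1 are also not strictly incompatible. Consecutive patients among those with usable records is a coherent, though weaker, definition. What is missing is a statement of which definition applies.

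**Conclusion.** The point holds as a risk built into the entry rule. Section 3.1 conditions entry on data availability, does not limit this to baseline, and does not reconcile it with the promise of consecutive starters. Applied as written, it permits selection on follow-up, with upward bias in the 12-month proportion as the more likely result. Consent may add to this to an unknown extent.

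The size cannot be derived from the documents. The ranges in the table rest on assumed values for the share left out and for remission among those left out. They run from nothing to well above the sampling error. The point deserves correction before data extraction because patients who are never entered cannot be recovered at the analysis stage.

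**What to change.** - **Entry.** In section 3.1, limit the data condition to the baseline data needed to confirm eligibility and the first risankizumab dose. Enter every consecutive eligible starter up to the cut-off.
- **Denominator.** For the primary endpoint, use all starters with at least 12 months since the first dose. Count documented discontinuation for failure or intolerance, Crohn's disease surgery, or death before 12 months as not in remission.
- **No evaluable marker.** For patients still on treatment without an evaluable 12-month marker, show the result both as non-remission and as observed. Counting them all as failures could bias the rate downward.
- **Accounting.** Report the number of starters not entered, with reasons, including lack of consent.
- **Ethics.** Ask the ethics committee how deceased or untraceable patients may be handled.

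The denominator and marker rules could sit in a statistical analysis plan, but the entry rule has to be changed in the protocol. The cost is rewording sections 3.1 and 4.4, one ethics query and a little more record screening. The headline rate is likely to be less favourable and may be conservative.
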